### **11.8.2. Between groups assessment**

Exploratory comparisons between the pooled RSV vaccine group and the pooled comparator group will be done in terms of the percentage of subjects, overall doses, reporting any Grade 2/3 AE during the 7-day follow-up period (Day 1-7) after vaccination, and/ or any fever  $>39.0^{\circ}\text{C}$  during the 7-day follow-up period (Day 1-7) after vaccination, and/ or any vaccine-related SAE during the 7-day follow-up period (Day 1-7) after vaccination.

The standardized asymptotic 95% CI for the difference between the pooled RSV group and (minus) the pooled comparator group will be computed.

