## 5. STUDY COHORT

### 5.1. Number of subjects

The target will be to enroll approximately 150 infants likely to be previously unexposed to RSV with about 50 infants for each of three randomization groups. If necessary, the sample size *may* be increased through additional recruitment in order to achieve *a sufficient number of* RSV infected infants, with a negative RSV exposure status (at screening based on in-stream serological testing), in each RSV vaccine group. Dose 1 administration should be completed before the first RSV season and second dose will be given one month after the first dose (RSV seasons will be determined for each country based on local epidemiological data and documented in the SPM). The RSV season is defined as the period of the year when 70% of the RSV cases have occurred in previous years. For the calculation, where available, data from up to the ten previous years should be applied. If the data permit calculation of the actual date of the beginning of the season, rather than approximation to the nearest month, this is desirable. Refer to the SPM for RSV seasons per country. Refer to Section 11.4 for the determination of sample size **(Amended 1 August 2019)**.

*Overview of the screening plan:*

Upon completion of all screening procedures (refer to [Table 7](#)), the investigator will review the inclusion/exclusion criteria for each infant. Infants meeting all eligibility criteria will be enrolled in the study. Their screening information will be recorded on the appropriate screen of eCRF.

If the investigator believes there is a reasonable reason to do so, screening procedures may be repeated once only. All screening procedures may be repeated except the blood sampling for humoral response (neutralizing antibody titers against RSV-A, RSV-F protein antibody concentrations and palivizumab-competing antibody concentrations).

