##### **6.2.2.2.1. Study group and treatment number allocation**

The target will be to enroll approximately 150 infants. Approximately 50 infants likely to be previously unexposed to RSV will be randomly assigned to receive 2 doses at 0, 1 month schedule of 0.5 mL of the ChAd155-RSV vaccine ( $5 \times 10^{10}$  vp) [the 2D RSV + comparator group], approximately 50 infants likely to be previously unexposed to RSV will be randomly assigned to receive a single dose of 0.5 mL of ChAd155-RSV vaccine ( $1.5 \times 10^{10}$  vp) [the 1D RSV + comparator group], and approximately 50 infants likely to be previously unexposed to RSV will be randomly assigned to receive 0.5 mL of the comparator/Placebo control vaccine [the comparator/Placebo control alone group].

Allocation of the subject to a study group at the investigator site will be performed using a randomization system on internet (SBIR) operated at the study level.

The randomization algorithm will assign each subject to the 2 doses of RSV vaccine + comparator group, the single dose of RSV vaccine + comparator group, or its corresponding active control comparator group with the aim of keeping the ratio between the pooled 2 dose RSV + comparator group, the pooled single dose RSV + comparator group and the pooled comparator group at 1:1:1 in the entire study (see [Table 25](#) for a description of pooled groups).

Countries will be grouped into five levels according to the choice of comparator vaccine or Placebo, the randomization algorithm will use a minimization procedure accounting for country as a minimization factor and the grouping comparator/placebo as a stratification factor to attempt to maintain a 1:1:1 ratio as well within each level in the assignment of RSV + comparator vaccine versus comparator/Placebo control vaccine alone.

The actual randomization assignment the subject received (to one of five 2 dose of RSV + comparator vaccine groups, to one of five single dose of RSV + comparator vaccine groups, or to one of five comparator/Placebo control alone groups) will be able to be identified in SBIR.

After obtaining the signed and dated ICF from the subject's parent(s)/LAR(s) and having checked the eligibility of the subject, the delegated study staff will access SBIR. Upon providing the subject identification number and the age, the randomization system will determine the study group and will provide the treatment number to be used for the first dose.

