## 11.4. Determination of sample size

The sample size determination is based on the minimum number of subjects needed to allow detection of a serious ERD signal having a magnitude similar to that of the historic FI-RSV vaccine trials [Kim, 1969]. A total of 150 infants will be enrolled and randomized with 1:1:1 ratio to receive either 1 dose of the  $1.5 \times 10^{10}$  vp/dose ChAd-155 RSV vaccine [the 1D RSV + comparator group], 2 doses of the  $5 \times 10^{10}$  vp/dose ChAd-155 RSV vaccine [the 2D RSV + comparator group], or no ChAd-155 RSV vaccine [the comparator/Placebo control alone group].

[figure not shown]
An effect of vaccination on ERD will be monitored very closely. It is anticipated that at least 50% of subjects [Dunn, 2013] will have a negative RSV exposure status (at screening which will be assessed by in-stream serological testing of baseline samples). While the rate of RSV infection could be highly variable by season, a conservative rate of infection of 20% in the first season is assumed [Kutsaya, 2016]. Therefore, with 50 infants in each RSV vaccine group, it is anticipated to observe at least 5 infected infants with a negative RSV exposure status (at screening based on in-stream baseline serological testing) in each RSV vaccine group [ $50 \times 0.5 \times 0.2 = 5$ ].

With a one-sided type I error of 0.05, and the assumption of a 10% rate of infection progressing to very severe RSV-LRTI (which is a conservative assumption based on the rate in the natural history of disease), 5 infections can provide at least 90% statistical power to demonstrate the progression rate from infection to very severe RSV-LRTI is less than 80%. That is less extreme than that observed in the historic FI-RSV vaccine trial where 80% of RSV RTI cases progressed to hospitalization [Kim, 1969]. During the course of the study, since the actual negative RSV exposure status (at screening based on in-stream baseline serological testing) and infection rates may be lower than 50% and 20%, respectively, the sample size **may** be adjusted as needed through additional recruitment in order to achieve **a sufficient number of** RSV infected infants with a negative RSV exposure status (at screening based on in-stream baseline serological testing) in each RSV vaccine group (**Amended 1 August 2019**).

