#### 11.5.4. Pooled groups in the study

All subjects in the single dose (1D,  $1.5 \times 10^{10}$  vp) RSV + comparator vaccine groups will be pooled together as the pooled 1D RSV group, similarly, all subjects in the two dose (2D,  $5 \times 10^{10}$  vp) RSV + comparator vaccine groups will be pooled together as the pooled 2D RSV group, and all subjects in the comparator/Placebo control vaccine alone groups will be pooled together as the pooled comparator group ([Table 25](#)).

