## **11.9. Analysis of immunogenicity**

The primary analysis will be performed on the PPS for immunogenicity and, if in any pooled group the percentage of vaccinated subjects with serological results excluded from the PPS for immunogenicity is more than 10%, a second analysis will be performed on the ES. The results from immunogenicity analysis will be reported by the pooled RSV vaccine group and the pooled comparator group.

For the final analysis, the Adapted PPS for immunogenicity analysis will be used which allows the summary of immunogenicity results by time point. In summary table on the Adapted PPS for immunogenicity, PPS for immunogenicity at Day 61 will be used for Pre, Day 31 and Day 61 immunogenicity summary and PPS for immunogenicity at Day 365 for Day 365 immunogenicity summary.

The infants are monitored for RSV infection starting from dose 1 and therefore immunogenicity analyses can be adjusted to exclude those infants with an infection prior to sampling.

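### Section 11.8.2 compares one undefined pooled RSV vaccine group with the comparator; read literally, it averages the one-dose and two-dose regimens in the only between-group comparison of general AEs, fever above 39.0°C and vaccine-related SAEs

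*Protocol*

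**What the plan says.** The design has three arms: "about 50 infants for each of three randomization groups" (section 5.1) and "A total of 150 infants will be enrolled and randomized with 1:1:1 ratio" (section 11.4). Section 11.5.4 and Table 25 build the analysis groups to match. All one-dose subjects "will be pooled together as the pooled 1D RSV group", all two-dose subjects "will be pooled together as the pooled 2D RSV group", and all control subjects form the pooled comparator. No group combining 1D and 2D is defined.

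Section 11.8.2 then states: "Exploratory comparisons between the pooled RSV vaccine group and the pooled comparator group will be done". The outcomes are any Grade 2/3 AE, fever above 39.0°C and vaccine-related SAEs in Days 1-7, as percentages of subjects over all doses. The interval is fixed in one sentence: "The standardized asymptotic 95% CI for the difference between the pooled RSV group and (minus) the pooled comparator group will be computed".

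Section 11.9 uses the same singular. Immunogenicity results "will be reported by the pooled RSV vaccine group and the pooled comparator group", although 11.9.1.1 asks for three pooled groups.

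Section 6.2.2.2.1 allocates by minimization on country with "the grouping comparator/placebo as a stratification factor", aiming at 1:1:1 within each of five levels. Section 11.8.2 does not mention these strata. Section 11.11 calls all comparative analyses exploratory, without multiplicity adjustment.

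**The concern.** The primary objective (section 2.1) covers safety and reactogenicity of the vaccine given as one dose or as two, and section 1.2.1 calls comparing the two regimens an important aspect of the study. The regimens differ widely: 2 × 5x10^10 = 10x10^10 vp against 1.5x10^10 vp, a ratio of about 6.7, and 1D infants receive formulation buffer at Day 31. Section 1.1.7 reports that in adults the higher dose seemed more reactogenic than a lower one (5x10^10 against 5x10^9 vp), so equal reactogenicity is not a safe default.

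For early AEs, fever and vaccine-related SAEs, 11.8.2 is the only place where vaccine and control are formally contrasted. If the analyst takes the singular group literally, the contrast answers for a mixture of regimens that no infant receives and cannot say which regimen carries an excess.

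**Working it through.** **Wording, side by side.**

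| Place | RSV grouping |
|---|---|
| 11.5.4, Table 25 | pooled 1D and pooled 2D, separate |
| Table 23, rules 2a-2c | either of two pooled RSV groups |
| 11.9.1.1 | three pooled groups |
| 11.9.1.2 | two pooled RSV groups |
| 11.10 | each of two pooled RSV groups against control |
| 11.8.2 | one pooled RSV group |
| 11.9, opening | one pooled RSV group |

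The Amendment 1 log in Appendix E, where the third arm was added, shows Table 23, 11.9.1.1, 11.9.1.2 and 11.10 converted to the new design. Neither that log nor the later ones lists a change to 11.8.2. The singular is most plausibly leftover two-arm text.

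**The plan's own figures.** Section 11.8.2 gives none. Section 11.4 gives safety precision per RSV group of 50, and it reproduces:
- P(at least one SAE at 5%) = 1 - 0.95^50 = 0.923 (stated: about 92%).
- Maximum exact 95% CI width: 28.9 points at n = 50 (stated: under 30) and 34.6 at n = 35, i.e. after 30% attrition (stated: 35).

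The plan therefore sized its safety statements by regimen.

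**What a merged contrast estimates.** Let e1D and e2D be each regimen's excess over the comparator. With 50 infants per arm:

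(50·p1D + 50·p2D)/100 - pC = (e1D + e2D)/2

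If e1D = 0, this is e2D/2. If e1D = e2D, it is unchanged.

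**Size.** The protocol gives no AE rates, so all rates here are assumptions. I take the standardized asymptotic interval to be the Miettinen-Nurminen score interval.

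| Events of 50: comparator / 1D / 2D | 2D minus comparator (95% CI) | Combined minus comparator (95% CI) |
|---|---|---|
| 5 / 5 / 15 | +20 (4.5 to 35.4) | +10 (-3.1 to 20.9) |
| 10 / 10 / 20 | +20 (2.0 to 37.0) | +10 (-5.4 to 23.4) |
| 10 / 15 / 20 | +20 (2.0 to 37.0) | +15 (-0.6 to 28.6) |
| 10 / 20 / 20 | +20 (2.0 to 37.0) | +20 (4.2 to 33.6) |

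No test is planned, but the chance that a two-sided 5% test would show a difference gives a second scale. The formula is Φ((d - 1.96·SE0)/SE1), with SE0 from the pooled rate and SE1 from the separate rates. At 10/10/30%:
- 2D against comparator: d = 0.20, SE0 = √(0.2·0.8·2/50) = 0.080, SE1 = √(0.3·0.7/50 + 0.1·0.9/50) = 0.0775, giving 71%.
- Combined: d = 0.10, SE0 = √(0.1667·0.8333·(1/100 + 1/50)) = 0.0645, SE1 = √(0.2·0.8/100 + 0.1·0.9/50) = 0.0583, giving 33%.

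Likewise 20/20/40% gives 59% against 25%, and 20/20/45% gives 77% against 35%. An intermediate 1D (20/30/40%) gives 59% against 47%. With equal regimens (20/40/40%), pooling helps: 59% against 70%.

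**Strata.** With 1:1:1 balance inside each comparator level, ignoring strata does not shift the crude difference. Assume equal-sized levels with event rates of 50, 30, 10, 10 and 10%, the same in all arms. The overall rate is 0.22 and p(1-p) = 0.1716. The mean within-level variance is (0.25 + 0.21 + 3·0.09)/5 = 0.146. The SE ratio is √(0.146/0.1716) = 0.92, so stratifying would shorten the interval by about 8%.

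**The case against.** The strongest reply is that merging is an inference. No text defines a combined group, neighbouring sections keep the regimens apart, and a careful analyst would follow Table 25. That is fair, and it makes this a defect of wording rather than a deliberate choice. But 11.8.2 twice names one RSV group and computes one difference, so the literal reading is open.

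A reader might infer three stronger things that the protocol does not support.

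- *That this is the only between-group safety comparison.* It is not. Section 11.10 gives relative risks for RSV-RTI, RSV-LRTI and severe LRTI for each RSV group against control, and 11.5.2 calls RSV-LRTI incidence a safety analysis.
- *That a two-dose signal would be lost to the trial.* Section 11.8.1 tabulates solicited AEs, fever and unsolicited AEs for each RSV + comparator group, and holding rules 2a-2c apply to either regimen on unblinded data. The cover is incomplete. The 11.8.1 sentence on SAEs and AEs of special interest reports only pooled groups, with the same loose RSV label. Rules 2a and 2b need Grade 3 events lasting at least 48 hours in at least 25% of infants, while 11.8.2 also covers Grade 2.
- *That ignoring the randomization strata causes the dilution.* It does not; under balanced allocation it costs some precision. The section is silent on stratification rather than excluding it. A stratified overall difference would still depend on country mix, because the control product differs by stratum.

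It also stands that the comparison is exploratory, and that the halving is the extreme case in which 1D has no excess.

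**Conclusion.** The point holds as an inconsistency with a practical consequence. Section 11.8.2 uses a group that Table 25 does not define and, read literally, reports the average excess of two very different regimens. The loss ranges from none (equal reactogenicity) through a quarter of the 2D excess (1D halfway between control and 2D) to one half (excess confined to 2D). In the 2D-only scenarios above, the chance of showing a difference falls from 59-77% to 25-35%. These sizes rest on assumed AE rates and 50 infants per arm. The consequence is confined to one exploratory comparison of early AEs, fever and related SAEs; the enhanced-disease analysis is already by regimen. It is worth correcting, but it does not threaten the trial's main safety conclusion.

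**What to change.** In 11.8.2, state that two differences are estimated, pooled 1D RSV minus pooled comparator and pooled 2D RSV minus pooled comparator, each with a standardized asymptotic 95% CI. A combined RSV contrast may be kept in addition, defined explicitly as 1D plus 2D. Align the singular wording in 11.8.1 and 11.9 with Table 25 and 11.9.1.1, so that SAE and AESI tables are also clearly by regimen.

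As a secondary refinement for precision only, stratify the interval by the comparator/placebo grouping used in randomization, collapsing sparse levels; about 50 infants per arm may be spread over five.

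Cost: an edit to the text and one more exploratory column. Each contrast rests on about 50 rather than 100 RSV recipients. At equal rates the SE grows by √((1/50 + 1/50)/(1/100 + 1/50)) = √(0.04/0.03) = 1.15, about 15%, and keeping the combined contrast as an addition preserves the narrower interval for the case where the regimens behave alike.

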## **11.9. Analysis of immunogenicity**

The primary analysis will be performed on the PPS for immunogenicity and, if in any pooled group the percentage of vaccinated subjects with serological results excluded from the PPS for immunogenicity is more than 10%, a second analysis will be performed on the ES. The results from immunogenicity analysis will be reported by the pooled RSV vaccine group and the pooled comparator group.

For the final analysis, the Adapted PPS for immunogenicity analysis will be used which allows the summary of immunogenicity results by time point. In summary table on the Adapted PPS for immunogenicity, PPS for immunogenicity at Day 61 will be used for Pre, Day 31 and Day 61 immunogenicity summary and PPS for immunogenicity at Day 365 for Day 365 immunogenicity summary.

The infants are monitored for RSV infection starting from dose 1 and therefore immunogenicity analyses can be adjusted to exclude those infants with an infection prior to sampling.

### **11.9.1. Within groups assessment**

#### **11.9.1.1. Analysis of secondary objectives**

For three pooled groups, at each timepoint that blood samples are collected for humoral immune response against the investigational RSV vaccine (neutralizing antibody titers against RSV-A, RSV F antibody concentrations).

- Geometric mean titers/concentrations (GMTs/GMCs) will be tabulated with 95% CI and represented graphically.
- Percentage of subjects above the seropositivity threshold will be tabulated with exact 95% CI.
- Antibody titers/concentrations will be displayed using reverse cumulative curves.

- The distributions of neutralizing antibody titers/concentrations will be tabulated.
- Percentage of responders in terms of neutralizing antibody titers will be tabulated with exact 95% CI.
- Individual post-vaccination versus pre-vaccination results will be plotted using scatter plots. Results of the comparator group will be used as a reference.
- Geometric mean of ratios of antibody titers/concentrations at each post-vaccination timepoint over pre-vaccination will be tabulated with 95% CI.
- Distribution of the fold increase of the neutralizing antibody titers will be tabulated by pre-vaccination titer category.
- The kinetics of individual antibody titers/antibody concentrations results will be plotted as a function of time for subjects with results available at all timepoints.

An immunogenicity analysis will also be performed on the ES with a negative RSV exposure status (at screening based on in-stream baseline serological testing) for whom immunogenicity data are available.

At study end a sensitivity analysis of immunogenicity will be performed on infants by baseline values.

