### 1.2.2.3. *In-stream serological testing of baseline samples to determine exposure status (Amended 1 August 2019)*

Subjects will not be screened for serostatus as criterion for enrolment in the study, due to the potential presence and detection of residual maternal antibodies (Refer to Section 6.7.3 for more details on the determination of a negative RSV exposure status). The assumption is that the majority of infants are previously unexposed (see Section 1.2.2.2). Serological testing of baseline samples to determine exposure status will be performed in-stream to ensure at least 50% of infants with a negative RSV exposure status (at screening based on in-stream baseline serological testing) and the sample size may be adjusted as needed through additional recruitment (Section 11.4).

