## 2.2. Secondary objectives

- To evaluate the occurrence of RSV respiratory tract infections *of any severity* from Visit 1 (Day 1, after Dose 1) up to the end of the first RSV transmission season, in infants aged 6 and 7 months.
- To evaluate the safety of the RSV investigational vaccine when administered IM as one ( $1.5 \times 10^{10}$  vp) dose or as two ( $5 \times 10^{10}$  vp) doses according to a 0, 1-month schedule, from study start (Day 1) up to the end of the second RSV transmission season in infants aged 6 and 7 months.
- To evaluate the occurrence of RSV respiratory tract infections from Visit 1 (Day 1, after Dose 1) up to the end of the second RSV transmission season, in infants aged 6 and 7 months.
- To evaluate the occurrence of very severe RSV-LRTI from Visit 1 (Day 1, after Dose 1) up to the end of the first RSV transmission season in RSV infected infants aged 6 and 7 months with a negative RSV exposure status (at screening based on in-stream baseline serological testing).
- To evaluate the humoral immunogenicity induced by the RSV investigational vaccine when administered IM as one ( $1.5 \times 10^{10}$  vp) dose or as two ( $5 \times 10^{10}$  vp) doses according to a 0, 1-month schedule, from study start (Day 1) up to the end of the first RSV transmission season, in infants aged 6 and 7 months.

Refer to Section [11.2](#) for the definition of the secondary endpoints.

[figure not shown]

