### 11.6.3. Immunogenicity

Any missing or non-evaluable immunogenicity measurement will not be replaced:

- For the within-group assessment, the descriptive analysis performed for each assay at each timepoint will exclude subjects with a missing or non-evaluable measurement. Kinetics will be plotted on subjects with results available at all timepoints.

The geometric mean titers/concentrations (GMTs/GMCs) will be computed by taking the anti-logarithm of the arithmetic mean of the log10 transformed titers/concentrations.

A seronegative subject will be defined as a subject whose antibody titer/concentration is below the cut-off value of the assay. A seropositive subject is a subject whose antibody titer/concentration is greater than or equal to the cut-off value of the assay.

Determination of a negative RSV exposure status in infants at 6 to 7 months of age will be based on RSV A and/or B neutralizing antibody titers present in serum at screening (before vaccination with the RSV vaccine) based on in-stream baseline serological testing. At birth, newborns do show positive for neutralizing antibodies due to maternal transfer during gestation. The titer of these antibodies declines over time. At the age of 6 to 7 months a cut-off can be defined below which infants are considered to have a negative RSV exposure status. Infants that show neutralizing antibody titers above this cut-off are suspected to have experienced a recent RSV infection. This cut-off will thus allow the discrimination between a negative RSV exposure status versus RSV infected infants before start of vaccination.

The description of the handling of data below the lower limit of quantification for GMC calculation and fold increase will be described in the statistical analysis plan.

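### Section 11.9 plans only within-group antibody summaries while maternal antibody is declining; a baseline-adjusted ratio to the concurrent comparator, with a CI, should be added

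*Protocol*

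**What the plan says.** The objective in Protocol Section 2.2 is causal in wording: "To evaluate the humoral immunogenicity induced by the RSV investigational vaccine when administered IM". Section 1.2.6 gives immunogenicity as one of the reasons for having a control group.

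Section 11.9 has a single analysis heading, the within-groups assessment (11.9.1). Its list of summaries opens "For three pooled groups, at each timepoint that blood samples are collected for humoral immune response against the investigational RSV vaccine" and includes geometric means, seropositivity, responder percentages, fold-increase distributions and this item: "Geometric mean of ratios of antibody titers/concentrations at each post-vaccination timepoint over pre-vaccination will be tabulated with 95% CI". The scatter-plot item adds "Results of the comparator group will be used as a reference". Baseline is addressed by tabulating fold increase by pre-vaccination titre category, and by this sentence: "At study end a sensitivity analysis of immunogenicity will be performed on infants by baseline values".

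On maternal antibody, Section 1.2.2.3 explains that serostatus is not an enrolment criterion "due to the potential presence and detection of residual maternal antibodies", and Section 11.6.3 states: "The titer of these antibodies declines over time". On natural infection during follow-up, Section 11.9 says that "immunogenicity analyses can be adjusted to exclude those infants with an infection prior to sampling".

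Other endpoints do get a contrast with control. Section 11.8.2 gives a 95% CI for RSV minus comparator on selected safety outcomes, and Section 11.10 gives a relative risk for each RSV group against control. Section 11.11 labels comparative analyses exploratory.

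**The concern.** A rise over baseline measures what the vaccine induced only if the titre would have stayed level without vaccine. The protocol says it would not, because whatever maternal antibody is in the screening sample is falling. In infants with measurable maternal antibody, the post/pre ratio in a vaccine group mixes induction with decay and understates induction. At Visit 7 natural RSV infection pushes the other way.

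The randomised comparator group is subject to the same decay, so the vaccine-to-comparator ratio is the quantity that answers the objective. It is not among the planned estimates. A reader would have to divide two tabulated values, with no interval for the quotient and no allowance for chance differences in baseline titre among about 50 infants per group. This matters because Section 1.2.1 calls comparison of the two regimens an important aspect of the study, and Section 1.2.3 foresees taking both, if tolerated, into the target population.

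**Working it through.** **The plan's own figures.** The protocol gives no sample size, power or precision for immunogenicity. Section 11.4 concerns progression to very severe RSV-LRTI. Its power of at least 90% reproduces as P(X ≤ 1 of 5 | 0.10) = 0.9^5 + 5 × 0.1 × 0.9^4 = 0.919, but it does not bear on this point.

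**Time between samples (Table 24).**
- Screening to Visit 1: 0–30 days. Visit 1 to Visit 3: 23–44 days. Visit 1 to Visit 5: 60–81 days.
- Screening to Day 31 sample: 0 + 23 to 30 + 44 = 23–74 days.
- Screening to Day 61 sample: 0 + 60 to 30 + 81 = 60–111 days.

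**Relation.** Without infection, let d = 0.5^(t / half-life) be the comparator post/pre ratio, and let E be the fold effect of vaccine relative to comparator. Then:
- vaccine-group post/pre ratio = E × d
- vaccine ratio ÷ comparator ratio = E

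**Inputs not fixed by the documents.** No half-life is given; 20 to 90 days is assumed. E = 2.4 is for illustration only and is borrowed from the adult RSV-A neutralizing rise in Section 1.1.7.

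| Assumed half-life | d at 30 days | 2.4 × d | d at 60 days | 2.4 × d | True effect that shows as 1.0 at 60 days |
|---|---|---|---|---|---|
| 20 days | 0.35 | 0.85 | 0.12 | 0.30 | 8.0 |
| 30 days | 0.50 | 1.20 | 0.25 | 0.60 | 4.0 |
| 40 days | 0.59 | 1.43 | 0.35 | 0.85 | 2.8 |
| 60 days | 0.71 | 1.70 | 0.50 | 1.20 | 2.0 |
| 90 days | 0.79 | 1.90 | 0.63 | 1.51 | 1.6 |

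Sixty days is the shortest interval allowed. At 111 days even a 90-day half-life gives d = 0.5^(111/90) = 0.43, and 2.4 × 0.43 is about 1.0.

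**Limit of the remedy.** The neutralization cut-off is 18 ED60 (Table 10), and decline below it is not measured. A simulation set values below 18 to 9, with log10 SD 0.5, baseline geometric mean 20 to 200, and half-lives of 30 and 40 days (all assumed). The vaccine-to-comparator ratio at 60 days was about 1.4 to 2.4 for a true 2.4. The contrast removes the decay bias but can be attenuated when many titres are below the cut-off.

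**Precision of the contrast.** With 50 per group, SE on the log10 scale = SD × √(2/50) × k, where k = √(1 − ρ²) for analysis of covariance and √(2(1 − ρ)) for a difference in change. With assumed SD 0.4 and ρ = 0.5, the first is 0.4 × 0.2 × 0.866 = 0.069, and the 95% CI is the estimate multiplied and divided by 10^(1.96 × 0.069) = 1.37. For ρ = 0.2 / 0.5 / 0.8 this factor is 1.42 / 1.37 / 1.24, against 1.58 / 1.43 / 1.26 for the difference in change.

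**Visit 7.** If 20% are infected (the Section 11.4 rate) with an assumed 8- to 32-fold rise, the group geometric mean is multiplied by 8^0.2 = 1.5 to 32^0.2 = 2.0. The comparator group is exposed too, so its parallel value shows the same kind of shift.

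**The case against.** The strongest reply is that the plan already contains most of what is needed. A reader might infer from the scatter-plot sentence that the comparator serves only as a plot reference. That is not supported: the whole list applies to three pooled groups, so geometric means and post/pre ratios with 95% CIs appear for the comparator too. If decay took the comparator to 0.25 and vaccinees to 0.60, both would be on the page and their quotient, 2.4, would be visible.

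Nor do the documents support saying that the vaccine is judged by its rise over baseline. The analysis is descriptive, the ratio is one of several summaries, and there is no success criterion. Baseline is not ignored either: there is the table by titre category, the sensitivity analysis by baseline values, and a separate analysis in infants with negative exposure status. Randomisation balances baseline titre in expectation. Model details are often left to a statistical analysis plan, which may already hold this contrast.

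All of that stands and limits the point. What remains is that the baseline analyses are still within-group, and infants below the exposure cut-off may still carry declining maternal antibody. No interval for the vaccine-to-comparator ratio is planned, although Sections 11.8.2 and 11.10 provide contrasts for safety and RTI. The protocol has itself fixed the within-group form, and Section 11.12 asks that departures be justified in the final report.

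A further fair objection is that excluding infected infants at Visit 7 conditions on a post-randomisation event that vaccination may influence. That also stands, so the exclusion can only be supportive.

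**Conclusion.** The point holds as an improvement that needs no new data, not as an error that invalidates the immunogenicity analysis. The estimate that answers the stated objective, a baseline-adjusted ratio to the concurrent comparator with its interval, is absent from Section 11.9.

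The direction of the bias at Days 31 and 61 follows from the protocol's own statements: the within-group ratio understates induction in antibody-positive infants. Its size cannot be established from the documents, because neither the maternal half-life nor the share of infants with measurable maternal antibody is given. The range of 0.30 to 1.51 for a true 2.4-fold effect at 60 days rests on assumed half-lives of 20 to 90 days and an adult fold rise used only as an example. It should not be read as a forecast, or as a claim that a real response would go unseen, since the comparator values stand beside it. At Visit 7 decay and infection pull in opposite directions, and the net bias of a within-group ratio could go either way.

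**What to change.** Add a between-groups assessment to Section 11.9, labelled exploratory in line with Section 11.11:

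- Analysis of covariance of log10 titre or concentration at Day 31, Day 61 and Visit 7, with regimen, baseline log10 value and comparator/placebo stratum as terms.
- For each assay and visit, report the geometric mean ratio of each pooled RSV group to the pooled comparator with 95% CI.
- Keep all within-group tables as they are.
- At Visit 7, report the ratio for all infants. As a supportive analysis, repeat it without infants PCR-positive for RSV before sampling, noting that this exclusion conditions on a post-randomisation event. This replaces the present optional wording.

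The cost is one model per assay and visit on data already collected, with no change to sample size, visits or samples. It is best fixed before the Day 61 analysis, when the statistician is unblinded (Section 11.12.1).
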